**Treatment Emergent (TE) Period:**

- For Treatment Period 1 of Part 1, the TE period will be from the first dose of study drug in Treatment Period 1 of Part 1 to the earliest of the following:
  - 1) 28 days after the date of subject's treatment completion during Treatment Period 1
  - 2) Safety Follow-up Visit if discontinued study early during Treatment Period 1
  - 3) 28 days after the last dose of the study drug for subjects who discontinued the study early during Treatment Period 1 and do not have a Safety Follow-up Visit
- For Treatment Period 2 of Part 1, the TE period will be from the first dose of study drug in the Treatment Period 2 of Part 1 to the earliest of the following:
  - 1) The date of treatment completion of Treatment Period 2
  - 2) Safety Follow-up Visit if discontinued study early during Treatment Period 2
  - 3) 28 days after the last dose of the study drug for subjects who discontinued the study early during Treatment Period 1 and do not have a Safety Follow-up Visit
- For Part 2, the TE period will be from the first dose of study drug in Part 2 to the earliest of the following:
  - 1) The Safety Follow-up Visit,
  - 2) 28 days after the last dose of the study drug for subjects who discontinued the study during Part 2 and do not have a Safety Follow-up Visit,

**Visit Windowing Rules:** Appendix C defines the windows for protocol-defined visits. The windows will be applied using the following rules for both scheduled and unscheduled visits. If no measurement is available within a visit window, the assessment will be considered missing for the visit. If there is more than one measurement available within the same visit window, the following rules will be used:

- For all safety parameters, if there are multiple measurements within a visit window, then 1) the record closest to the target day will be used, with the exception of the threshold analysis in which the worst record will be used; 2) if there are multiple records within the same distance of the target day, the latest record will be used; or 3) the Safety Follow-Up (SFU) visit will not be windowed; instead, the nominal visit will be used in relevant analyses.
- For all efficacy parameters, if there are multiple measurements within a visit window, the record at the scheduled visit will be used. Otherwise,
  - If there are no measurements at the scheduled visit, then the record closest to the target day will be used;

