  - If there are multiple records with the same distance to the target day, the latest record will be used.
  - Assessments at the early treatment termination (ETT) visit will follow the windowing rules for regular visits.
  - Assessments at safety follow-up (SFU) visit will follow the windowing rules for regular visits if they fall within the upper boundary of the window for the last scheduled visit; it will remain as the SFU if it goes beyond the upper boundary of the window for the last scheduled visit.

**Incomplete/Missing data:** Missing data (e.g., dates) will remain as missing in the listings, and conservative conventions established will be used to derive specified parameters for summaries.

**Outliers:** No formal statistical analyses will be performed to detect and/or remedy the presence of statistical outliers.

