## Appendix C: Visit Window Mapping Rules for Efficacy and Safety Measurements

*Table 10-4 Visit Window Mapping Rules (within Period)*

Assessments	Period - Visit	Analysis Visit	Target Study Day	Visit Window (in study days)

 
• Labs               
 
○ Chemistry
 
○ Hematology
 
○ Liver Function Tests
 
○ Weight, Height.
 
 
 
	1 - Day 1	Day 1	1	[1, 1]
	1 - Week 8	Week 8	57	[2, 85]
	2 - Week 16	Day 1	1	[1, 1]
	2 - Week 24	Week 8	57	[2, Date of Week 24 visit]
	2 – Safety Follow-up Visit	Safety Follow-up Visit	NA	Use the nominal visit name

 
• LCI
 
	1 - Day 1	Day 1	1	[1, 1]
	1 - Week 4	Week 4	28	[2, 42 ]
	1 - Week 8	Week 8	57	[43, 85]
	2 - Week 16	Day 1	1	[1, 1]
	2 - Week 20	Week 4	28	[2, 42 ]
	2 - Week 24	Week 8	57	[43, Date of Week 24 visit]
	2 – Safety Follow-up Visit	Safety Follow-up Visit	NA	Use the nominal visit name

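### When the scheduled Week 8 weight is missing, SAP Appendix C reports a Week 4, Week 20 or early-termination weight as Week 8 (minor)

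*SAP*

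**What the plan says.** SAP 9.1 (Visit Windowing Rules) puts the scheduled visit first: "For all efficacy parameters, if there are multiple measurements within a visit window, the record at the scheduled visit will be used". Only when that record is absent does the fallback apply: "If there are no measurements at the scheduled visit, then the record closest to the target day will be used". Unscheduled records are eligible ("The windows will be applied using the following rules for both scheduled and unscheduled visits"), and so are early-termination records: "Assessments at the early treatment termination (ETT) visit will follow the windowing rules for regular visits".

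SAP Appendix C sets the windows, with a Week 8 target of Day 57:

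| Parameter | Week 4 window | Week 8 window, Period 1 | Week 8 window, Period 2 |
|---|---|---|---|
| Weight, height (listed with labs) | none | Days 2 to 85 | "2, Date of Week 24 visit" |
| LCI | Days 2 to 42 | Days 43 to 85 | "43, Date of Week 24 visit" |

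SAP Appendix B schedules height and weight at Weeks 4 and 20 (Table 3-2) and at the early-termination and Safety Follow-up visits (Table 3-3). SAP 6.1.2 defines the weight and BMI endpoints after 8 weeks of treatment.

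On Safety Follow-up records the SAP gives three instructions. For efficacy parameters, SAP 9.1 windows them like regular visits up to the upper boundary of the last scheduled visit's window. For safety parameters, SAP 9.1 does not window them. Appendix C says "Use the nominal visit name", but only in a Period 2 row.

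**The concern.** The weight window opens the day after the first dose and, in Period 1, closes four weeks after the target. If the Week 8 weight was not taken, almost any other weight in the period can fill the slot, and nothing in the summary would show it. The result is a change over four weeks, or up to early termination, reported as the change over eight. Weight and BMI get summary statistics and a listing only (SAP 9.3.2), so no model accounts for the timing. In a small study one child is visible in the mean. The separate Week 4 window for LCI shows that the SAP could have kept the two visits apart for weight as well.

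**Working it through.** **1. The plan's own figure.** Week 8 = 8 × 7 + 1 = Day 57, which matches Appendix C. The protocol allows ±5 days at Week 8 (Table 3-2), so an on-time visit falls on Days 52 to 62, a span of 11 days. The Period 1 weight window spans 85 − 2 + 1 = 84 days.

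**2. The rule applied to weight, Period 1** (scheduled record first, then closest to Day 57, ties to the latest record):

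| Weights available | Reported as Week 8 |
|---|---|
| Week 4 (Day 29), Week 8 (Day 57) | Day 57, as intended |
| Week 4 only, on any of Days 25 to 32 | the Week 4 weight |
| Early termination only, Day 20 | Day 20 |
| Week 4 (Day 29), early termination (Day 36), Safety Follow-up (Day 63, last dose Day 35) | Day 63 under the efficacy rule; Day 36 under the safety rule |

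The second and third rows do not depend on which rule governs weight, because both take the closest record in the window. In Period 2 the same logic turns a Week 20 weight into Week 8 if the Week 24 visit took place without a weight. If that visit never took place, the window has no defined end.

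**3. Size for one child.** Share of the 8-week change under linear growth = (day − 1)/56:

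- Day 29: 28/56 = 50%
- Day 43: 42/56 = 75%
- Day 62: 61/56 = 109%

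The documents give no growth rate, so I assume 1.5 to 2.5 kg/year. The 8-week change is then 1.5 × 56/365.25 = 0.230 kg to 2.5 × 56/365.25 = 0.383 kg. A Week 4 weight is short by half of that, 0.115 to 0.192 kg.

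**4. Size in the mean.** The final N is not in the documents, so I assume 5 to 20. The shift per affected child runs from 0.115/20 = 0.006 kg to 0.192/5 = 0.038 kg. As a share of the 8-week change this is 50%/N, or 2.5% to 10%.

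**5. How many children.** The 10% Part 1 dropout in SAP 7.2, applied to 5 to 20 children, gives 0.5 to 2. This is a rough guide only: SAP 7.1 has children who stop drug keep attending, which lowers it.

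**6. Safety Follow-up, Period 1.** The visit falls 21 to 35 days after the last dose. At +28 days it lies inside Days 2 to 85 for any last dose up to Day 57 (85 − 28). I ran through last-dose days 1 to 57, early-termination delays of 0 to 20 days and all follow-up timings, with an early-termination weight present. The latest follow-up weight selected is Day 74: last dose and early termination on Day 39 (18 days from target), follow-up on Day 74 (17 days from target). That is 73/56 = 130% of the 8-week change.

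**7. LCI, Period 1.** The window ends 85 − 62 = 23 days past the protocol's limit, in washout. If an off-drug value replaced Week 8 and had lost the whole effect, the child's Week 4/Week 8 average would lose half of it: 0.50 to 0.75 points for the plan's effects of 1.0 and 1.5. The mean shift is effect/(2N), from 1.0/40 = 0.025 to 1.5/10 = 0.15 points. The largest fall in the posterior probability, over the effect and SD pairs in SAP Table 7-1 and N of 5 to 20 with the SD held fixed, is at effect 1.0, SD 2.2, N = 5. The standard error is 2.2/√5 = 0.984, so t goes from 1.016 to 0.915 on 4 df, and the probability from 0.817 to 0.794, a fall of 0.023.

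**The case against.** The best defence is that the fallback seldom operates. A scheduled record always wins, children who stop drug are asked to keep attending, and weight is easy to obtain at any attended visit. These endpoints are descriptive, each value is also listed, and the shift in the mean is small. All of that stands, and it is why the point is minor. It does not alter what the rule does when the scheduled weight is missing.

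A second objection is that weights at Weeks 4 and 20 rest on one copy of the schedule. The SAP's row has 16 marks and is blank only under washout. The protocol's row shows 13 in the text version, where its clinic-visit row also shows too few (14). I rely on the SAP copy; the sponsor should confirm it. The early-termination route does not depend on it.

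Three stronger readings are tempting, and the documents do not support them.

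- *Off-drug LCI values threaten the primary analysis.* No breath washout test is scheduled between Weeks 8 and 16, and Table 3-3 lists none at early termination or follow-up. It takes a missing scheduled Week 8 test together with a late or unscheduled one in washout, and SAP 9.3.1 sets no success criteria. Nor is the bias sure to run against ivacaftor: a test taken during illness after placebo could raise the placebo value. A Week 4 LCI taken by Day 42 is never relabelled.
- *A Day 85 weight, at 150% of the 8-week change, is typical.* It needs a skipped or late early-termination weight, or an unscheduled one.
- *A Safety Follow-up weight certainly enters.* Appendix C lists weight with the labs, and safety parameters are not windowed at that visit. It enters only if weight is handled under the efficacy rule, which is a fair reading for a secondary efficacy endpoint but not the only one.

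**Conclusion.** The point holds as a minor one. For a child without a scheduled Week 8 or Week 24 weight, the stated rules put a Week 4, Week 20 or early-termination weight under the Week 8 label. A Week 4 value understates that child's change by about half. The kilogram figures rest on linear growth, an assumed growth rate and an assumed N.

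Separately, the Safety Follow-up instructions need reconciling. In Period 1 the result depends on whether weight counts as efficacy or safety. In Period 2 the efficacy rule in SAP 9.1 conflicts with Appendix C for a follow-up visit that falls before the window closes. Two programmers could derive different datasets.

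The LCI window is a tidying matter only: its effect is at most about 0.023 in the posterior probability, by a route that needs an off-schedule test.

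**What to change.** In SAP Appendix C:

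- Separate weight and height from the labs. Give them a Week 4 window of Days 2 to 42 and start Week 8 at Day 43, in both periods. These are the boundaries already used for LCI.
- For weight, height and LCI in Period 1, close the Week 8 window at Day 62, or at the actual Week 8 visit date if that is later. This keeps a repeat measurement made within the protocol's +5 days.
- In Period 2 keep the Week 24 visit as the upper bound, and use period Day 62 if that visit was missed.
- Add a Period 1 Safety Follow-up row reading "Use the nominal visit name", and make the efficacy rule in SAP 9.1 agree with it.

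A value admitted on Days 43 to 62 carries 75% to 109% of the 8-week change under linear growth. The cost is a few lines of text and some table programming before database lock, with no change to visits or data collected. The price is that a few Week 8 values become missing instead of mistimed.

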**Data Presentation:**

Where applicable and possible, data will be presented by ivacaftor dose group (50mg, 75mg and 150mg), placebo and overall ivacaftor dose group. For summary statistics, descriptive statistics will be presented for each visit and change from period baseline.

**Unscheduled Visits:** Unscheduled visit measurements will be included in the following:

- derivations of measurements at scheduled visits per specified visit windowing rules;
- derivations of baseline/last on-treatment measurements;
- derivations of the maximum/minimum on-treatment values and maximum/minimum changes from baseline values for safety analyses;
- data listings where appropriate.

## 9.2 Background Characteristics

### 9.2.1 Subject Disposition

The subject disposition will be summarized in both a table and a listing. The number of subjects in the following categories will be presented:

- Randomized
- FAS
- Safety Set

The number and percentage (based on Safety Set) of subjects in each of the following disposition categories will be presented:

- Completed study drug treatment regimen of Part 1 Treatment Period 1
- Prematurely discontinued the treatment and the reason for discontinuations during Part 1 Treatment Period 1
- Completed study drug treatment regimen of Part 1 Treatment Period 2
- Prematurely discontinued the treatment and the reason for discontinuations during Part 1 Treatment Period 2
- Continue into Part 2
- Prematurely discontinued the study and the reasons for discontinuations

### 9.2.2 Demographics and Baseline Characteristics

Demographic and baseline characteristics data will be summarized in both a table and a listing based on Safety Set by treatment sequence.

Demographic data will include the following:

- Sex (female and male)
- Age
- Ethnicity (Hispanic or Latino, not Hispanic or Latino, and not collected per local regulations)
- Race (White, Black or African American, Asian, American Indian or Alaska Native, Native Hawaiian or Other Pacific Islander, and Other)
- Geographic region (by each country)

Baseline characteristics will include the following:

- Weight (kg)

- Height (cm)

- BMI (kg/m^2)

The following disease characteristics will be listed only:

- *CFTR* mutation at screening
- Ophthalmologic examinations at screening

### 9.2.3 Medical History

Medical history in this study will be coded by using the Medical Dictionary for Regulatory Activities (MedDRA).

Medical history data will be summarized descriptively by system organ class and preferred term based on Safety Set by the treatment group. The corresponding data listing will also be provided.

### 9.2.4 Prior and Concomitant Medications

Medications used in this study will be coded by using the World Health Organization Drug Dictionary Enhanced (WHODDE) and categorized as the following:

- **Prior medication:** any medication that started before the first dose of study drug, regardless of when it ended.
- **Concomitant medication:** medication continued or newly received during the TE period for Treatment Period 1 or Treatment Period 2. If a subject took a medication during a specific Treatment Period, this medication will be attributed to the study drug the subject received

during this Treatment Period. As a result, 1 medication could be attributed to more than 1 study drug for an individual subject.

- **Post-treatment medication:** medication continued or newly received beyond the TE period for Treatment Period 2, or between the TE periods for Treatment Period 1 and Treatment Period 2, or beyond the TE period for Treatment Period 1 for subjects who do not have Treatment Period 2.

Prior medications and concomitant medications will be listed only.

### 9.2.5 Study Drug Exposure

Exposure summaries will be based on the Safety Set.

Duration of study drug exposure is defined as: last dose date – first dose date + 1 day, regardless of any interruption in dosing between the first and the last dose for each treatment period. The duration will be calculated for the treatment corresponding to each treatment period.

Total exposure (in patient years) and duration of study drug exposure will be summarized descriptively (number, mean, SD, SE, median, minimum, and maximum). Total exposure is defined as the sum of the subject's duration of treatment exposure and expressed in patient years. Duration of exposure will also be summarized into categories as the following:  $\geq 1$  day,  $\geq 1$  week,  $\geq 2$  weeks,  $\geq 4$  weeks,  $\geq 8$  weeks.

### 9.2.6 Study Drug Compliance

Study drug compliance based on the number of tablets/sachets taken will be calculated as:  $100 \times [(\text{total number of study drug dispensed}) - (\text{total number of study drug returned})] / (\text{total number of study drug planned to be taken per day} \times \text{duration of study drug exposure in days})$ . The maximum percentage of study drug taken will be 100%.

Study drug compliance based on study drug exposure will be calculated as:  $100 \times [1 - (\text{total number of days of any study drug interruption}) / (\text{duration of study drug exposure in days})]$ .

Study drug compliance will be summarized descriptively by the number of subjects (n), mean, SD, SE, median, min, and max.

Study drug compliance summaries will be based on the Safety Set.

### 9.2.7 Important Protocol Deviations / Violations

An important protocol deviation and violation is a protocol deviation or violation that has the potential to affect the interpretation of study results. PD/PV will be identified from the clinical database and/or site deviation log.

The rules for identifying PD/PVs will be included in an internal Biometrics document.

All PD/PV will be presented as an individual subject data listing only.

### 9.3 Efficacy Analysis

#### 9.3.1 Analysis of the Primary Efficacy Variable

The primary efficacy variable is the absolute change from baseline through 8 weeks of treatment in LCI endpoint.

LCI will be summarized using descriptive statistics and will also be presented for each visit and change from period baseline.

Due to the low sample size of the study the planned MMRM analyses will not be carried out as the mixed effect model is likely to be unstable.

Because of the low expected power, a Bayesian analysis will be performed. A Bayesian analysis on within-subject treatment difference, i.e. difference between the averages of the week 4 and week 8 LCI measurements on ivacaftor and placebo. The Bayesian approach calculates the posterior probability that the treatment difference is less than zero, which can be obtained from a frequentist one sample t-test. There are no specific success criteria due to the low subject numbers available for analysis

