## **9.5 Replacement of Subjects**

Subjects who withdraw or are withdrawn during the study drug treatment period(s) will not be replaced.

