### **10.3 Method of Assigning Subjects to Treatment Groups**

#### **Part 1**

Subjects will be considered enrolled when they are determined to have met all eligibility criteria and are randomized to a treatment sequence (Sequence 1 or Sequence 2). Subjects will be randomized in a 1:1 ratio.

An interactive voice response system (IVRS)/interactive web response system (IWRS) will be used to assign subjects to treatment. Detailed instructions for randomization and randomization code generation will be provided separately.

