## **12.3.3 Part 1 Efficacy Analysis**

### **12.3.3.1 Analysis of Primary Variable**

The primary efficacy variable is the absolute change from baseline through 8 weeks of treatment in LCI endpoint. The analysis will be based on a mixed-effects model for repeated measures (MMRM) utilizing the FAS.

The model will include the absolute change from study baseline in each period as the dependent variable; sequence, treatment, period, and visit within period as fixed effects; LCI baseline and

age as covariates; and subject nested within sequence as the random effect. Unstructured covariance matrix is further assumed for the repeated measurements of the same subject within each period. If there is a convergence problem for the unstructured covariance matrix, an appropriate covariance matrix structure, such as compound symmetry, will be assumed in the primary analysis. The average treatment effect across all post-baseline visits within the treatment period will be obtained from the model. Comparative treatment assessment will be performed using the P value and 95% confidence interval (CI). Carry-over effect will be assessed by the sequence effect in the model.

Because of the low expected power, a Bayesian analysis may be performed. The analysis will compute the posterior probability that the treatment difference is greater than 0, based on a non-informative prior distribution. There are no specific success criteria due to the low subject numbers available for analysis.

Summary and individual listings of efficacy data will be generated. A more detailed description of the planned statistical analysis of efficacy endpoints will be presented in the SAP.

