### 3. SUMMARY OF MODIFICATIONS

#### 3.1 Modifications from the Approved Clinical Study Protocol

There are no modifications from the approved Clinical Study Protocol (CSP) (Version 4.0, 12 April 2017).

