## 7.2 Sample Size and Power

It is planned that up to a maximum of approximately 50 subjects will be enrolled in this study. As shown in Table 7.1, a sample size of 50 subjects will provide approximately 80% power to detect a treatment difference in mean change from study baseline in LCI (difference between ivacaftor and placebo in the change from study baseline) of 1.5 points. The calculation is based on a paired t-test with a 2-sided significance level of 0.05, and assumes that the within-subject standard deviation (SD) for the difference in change from study baseline for the 2 periods is 3.5 points, and that the dropout rate is about 10% for Part 1.

Different scenarios are presented in Table 7.1 for the variability and the magnitude of the treatment effect based on 80% power and 2-sided significance level of 0.05. The most conservative scenarios are presented in the last 2 rows of the table (i.e., treatment effect of 1.0 and 1.5, respectively).

**Table 7-1 Sample Size Calculation Corresponding to Different Values of Treatment Effect on Lung Clearance Index Change-From-Predose**

Treatment Effect (points) on LCI Change From Study Baseline	Standard Deviation of Paired Treatment Difference in LCI Change From Study Baseline	N
1.0	1.0	12
1.0	1.2	15
1.0	1.5	22
1.0	1.8	31
1.0	2.0	37
1.0	2.2	45

**Table 7-1 Sample Size Calculation Corresponding to Different Values of Treatment Effect on Lung Clearance Index Change-From-Pre-dose**

Treatment Effect (points) on LCI Change From Study Baseline	Standard Deviation of Paired Treatment Difference in LCI Change From Study Baseline	N
1.5	3.5	50

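### With the MMRM cancelled, the LCI posterior in SAP 9.3.1 carries no period adjustment; a period-adjusted posterior should be reported beside it, and SAP 3.1 corrected

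*SAP*

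**What the plan says.** Protocol 12.3.3.1 analyzes the primary LCI variable with an MMRM that has "sequence, treatment, period, and visit within period as fixed effects". The same section allows an optional Bayesian analysis with a non-informative prior and names no model terms for it.

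SAP 9.3.1 states that "the planned MMRM analyses will not be carried out as the mixed effect model is likely to be unstable". It makes the Bayesian analysis definite and defines its variable as the "difference between the averages of the week 4 and week 8 LCI measurements on ivacaftor and placebo". The posterior probability that this difference is below zero is one "which can be obtained from a frequentist one sample t-test". No period or sequence term appears, and neither document sets a threshold for success.

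SAP 3.1 nevertheless says: "There are no modifications from the approved Clinical Study Protocol".

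On the balance of the sequences, both documents give 1:1 randomization. Protocol 10.3 adds: "Detailed instructions for randomization and randomization code generation will be provided separately". Protocol 9.5 says: "Subjects who withdraw or are withdrawn during the study drug treatment period(s) will not be replaced". Enrollment was closed on 21 February 2017, short of the planned 50.

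**The concern.** The SAP gives a reason for dropping the mixed model: instability at a small sample size. That reason does not extend to the period adjustment, which needs only two sequence means and one pooled variance. As written, no inference on the primary endpoint in SAP 9.3.1 accounts for a shift in LCI between periods that begin 16 weeks apart in children aged 3 to 5.

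A one-sample test on treatment differences cancels a period effect only when the two sequences contribute equal numbers. Otherwise part of the shift is counted as drug effect, in a direction set by the sign of the shift and by which sequence is larger. The posterior is the only planned inference on the primary objective and has no success threshold, so readers will judge the number directly.

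**Working it through.** **Inputs from the documents.** SAP 7.2 and Protocol 12.1 give effect 1.5, SD of the paired difference 3.5, paired t-test, two-sided 0.05, 80% power and 10% dropout. The SAP "assumes that the within-subject standard deviation (SD) for the difference in change from study baseline for the 2 periods is 3.5 points". Table 7-1 also has a row with effect 1.0 and SD 2.2.

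**Assumed, because the documents do not give them.** N = 10 evaluable children; splits (Sequence 1 : Sequence 2) of 5:5, 4:6 and 3:7; π = +1 or −1 LCI point, where π is Period 2 minus Period 1.

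**1. The plan's own figure.** Noncentral-t power for effect 1.5 and SD 3.5 first reaches 80% at n = 45 (80.3%), and 45/0.9 = 50. The stated 50 reproduces. This calculation has no period term either.

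**2. Bias.** Let d be ivacaftor minus placebo within a child and τ the true effect. Study baseline cancels in d; a period effect does not.
- Sequence 1 (ivacaftor first): E(d) = τ − π
- Sequence 2 (placebo first): E(d) = τ + π
- Pooled mean: [n1(τ − π) + n2(τ + π)]/N = τ + π(n2 − n1)/N
- Unweighted mean of the two sequence means: τ, whatever the split

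For |π| = 1 the pooled bias is 0 at 5:5, 2/10 = 0.20 at 4:6 and 4/10 = 0.40 at 3:7.

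**3. Spread.** The pooled variance absorbs π: E(s²) = σ² + 4π²n1n2/[N(N − 1)]. At 5:5 and |π| = 1 the added term is 100/90 = 1.11. So 12.25 becomes 13.36 at SD 3.5, and 4.84 becomes 5.95 at SD 2.2. With equal sequences this is the only effect.

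**4. Error and posterior.** Pooled RMSE = √{[π(n2 − n1)/N]² + σ²/N}. Adjusted RMSE = (σ/2)√(1/n1 + 1/n2). For 3:7 at SD 3.5 these are √(0.16 + 1.225) = 1.177 and 1.75 × √(1/3 + 1/7) = 1.208. Median posteriors assume normally distributed differences. They come from numerical integration and agree with simulation within 0.002; the zero-effect row is from simulation.

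| Effect, SD | Split | Median P(difference < 0), pooled (π = +1 / −1) | Adjusted | RMSE, pooled v adjusted |
|---|---|---|---|---|
| −1.5, 3.5 | 5:5 | 0.893 / 0.893 | 0.900 | 1.107 v 1.107 |
| −1.5, 3.5 | 4:6 | 0.862 / 0.918 | 0.896 | 1.125 v 1.130 |
| −1.5, 3.5 | 3:7 | 0.825 / 0.939 | 0.882 | 1.177 v 1.208 |
| −1.0, 2.2 | 5:5 | 0.892 / 0.892 | 0.912 | 0.696 v 0.696 |
| −1.0, 2.2 | 4:6 | 0.844 / 0.929 | 0.908 | 0.724 v 0.710 |
| −1.0, 2.2 | 3:7 | 0.781 / 0.955 | 0.895 | 0.802 v 0.759 |
| 0, 2.2 | 3:7 | 0.30 / 0.70 | 0.50 | 0.802 v 0.759 |

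**5. Break-even.** The two RMSEs are equal at |π| = σ√[N/(4n1n2)], which is 0.32σ at 4:6 and 0.35σ at 3:7. At SD 3.5 that is 1.13 and 1.21 points, above the illustrative 1 point. At SD 2.2 it is 0.71 and 0.76 points, below it. This is why the two blocks of the table disagree about which estimate has the lower error.

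**The case against.** The case for leaving the analysis alone is substantial.

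- **Every trigger is assumed.** Nothing in the documents shows unequal sequences or any drift. Early closure and non-replacement make imbalance possible, no more. The protocol also limits drift, through antibiotic-cycle timing of visits (8.1) and conditions for entering Period 2 (8.1.4). This stands, and π = 1 may be high.
- **The pooled estimate is often the better one.** At SD 3.5 and |π| of 1 point or less it ties or has lower error at every split tested, and its 95% interval still covers about 94% to 96% of the time. This stands. Which estimate leads is a choice between bias and variance.
- **The protocol's Bayesian option has no period term to lose.** Correct: the adjustment belonged to the MMRM. A reader might infer that the SAP stripped a term from the protocol's Bayesian analysis, or hid the change of model. Neither is supported. SAP 9.3.1 cancels the MMRM openly and gives a reason, and a one-sample test matches the paired t-test used for planning.
- **Other outputs may reveal drift.** SAP 9.1 promises efficacy analyses on change from period baseline, which would remove a level shift already present at Week 16. This stands in part, because the SAP does not say that the posterior is repeated on that scale.
- **No decision rule depends on the number.** True, and it lowers the severity. It does not remove the point, since without a rule the posterior is all that readers have to weigh.

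**Conclusion.** The concern holds as a minor point. After SAP 9.3.1 no inference on the primary LCI endpoint adjusts for period, and the reason given for dropping the MMRM does not explain that loss. The bias formula is exact under an additive period effect with no carry-over. The point estimate is unbiased when evaluable sequences are equal, where the cost is a slightly inflated SD (0.893 v 0.900 at SD 3.5; 0.892 v 0.912 at SD 2.2).

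At unequal splits the shift can matter. In the 3:7 example at SD 2.2, drift and imbalance alone give an inactive drug a median posterior of 0.30 or 0.70. That size rests wholly on assumed N, split and π.

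A reader might infer that the planned posterior is biased, or that the adjusted estimate must replace it. The documents support neither: they give no split and no drift, and at the planning SD the pooled estimate does as well or better on error for |π| up to 1 point.

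The statement in SAP 3.1 is wrong whatever the value of π. It is an inaccurate declaration, not concealment.

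**What to change.** In SAP 9.3.1, prespecify a period-adjusted posterior beside the one-sample result. Base it on the unweighted mean of the two sequence-specific mean differences (two-sample crossover t-test, N − 2 df, same non-informative prior). For both analyses report the estimate, the 95% credible interval and P(difference < 0), with the number of evaluable subjects per sequence. The sponsor chooses which of the two leads and fixes that choice before database lock. In SAP 3.1, list the replacement of the MMRM as a modification of the protocol.

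The cost is SAP wording and a few lines of code on data already collected. The adjusted interval loses one degree of freedom and is wider at unequal splits. With no period effect, the mean 95% half-width goes from 0.70 to 0.71 SD at 5:5 and from 0.70 to 0.77 SD at 3:7. Keeping the pooled result alongside covers that loss. The change does not address carry-over.
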